## METHODS

---

### Study Overview

The TEAMS study was a cluster randomized, comparative effectiveness trial comparing the effectiveness of TeleCAM and DirectCAM delivered at 43 clinics across Alabama, Mississippi, and Tennessee. There were 40 clinics initially randomized and 3 satellite sites including Cookeville, Ashland City and Mobile were added later. These 3 satellite sites were not randomized as they were close to and were associated with support groups at the existing randomized sites. The satellites sites were recruited to alleviate logistical challenges in throughput around baseline testing after enrollment.

Using the clinics as the units of randomization, our criteria while identifying clinic sites were to minimize the risk of contamination while having enough sites for a cluster randomization, ability to detect a small to moderate effect size, and ability to recruit efficiently. The randomization list was run by a study statistician who was not involved in any participant interaction and intervention delivery. Given the nature of this study design, group assignments were not blinded to participants and study staff involved in the intervention delivery but were blinded to data analysts.

[figure not shown]
### Study Setting

#### Main Study

The clinical partners consisted of 5 occupational therapists and 83 physical therapists and assistants at 43 clinics in three States: 19 in Alabama, 16 in Mississippi and 8 in Tennessee. Of these 43 clinic sites, 5 of the sites were considered small towns or rural, 10 were considered

micropolitan, and 28 were considered urban metropolitan. All clinics were considered outpatient rehabilitation clinics; however, 4 were located within hospitals, 38 were considered private practice and one site was a comprehensive MS center. **Figure 1** highlights the geographic location of clinical partners within each state (Alabama, Mississippi, and Tennessee).

**Figure 1. Geographic Location of the TEAMS Clinical Partners (clinics= 43)**

## **Enhancement Study**

For the Enhancement study, participants received all testing through a teleassessment platform, followed by 20 synchronous telerehabilitation sessions in line with our original study design for the other two arms (TeleCAM, DirectCAM). A total of 8 physical therapists were involved in the testing and rDirectCAM delivery of the Enhancement study.

## **Participants**

The study population included people with MS in the states of Alabama, Mississippi, and Tennessee. Interested participants were enrolled if they self-reported a diagnosis of MS, with a PDDS score between 0 and 7. The PDDS is an ordinal scale ranging from 0 (Normal) to 8 (Bedridden). It is a simple and practical tool for measuring self-reported disability status for people with MS and has a strong correlation ( $rs=0.8$ ) with the Expanded Disability Status Scale (EDSS). Additional inclusion criteria included ages of 18 to 70 years, able to use arms and legs for exercise, and physician clearance. Exclusion criteria included: 1) significantly impaired acuity that prevented seeing a tablet screen to follow home exercise program; 2) cardiovascular disease event within the past six months, severe pulmonary disease, renal failure; 3) active pressure ulcer; 4) currently pregnant; 5) within 30 days of receiving an exercise or rehabilitation program; 6) Godin Leisure Time Exercise Questionnaire (GLTEQ) score  $\geq 24$ .

The GLTEQ contains two questions. The first question asks participants to report weekly frequencies of activities they perform at different intensities. A total weekly leisure activity is a sum of activity scores calculated by multiplying the weekly frequencies of strenuous, moderate, and light activities by 9, 5, and 3, respectively. The second question asks participants the

frequency of weekly leisure-time activities performed that are long enough to work up a sweat.

The scale has been validated and used in previous research with people with MS.

Adverse events (AEs) were monitored following types defined by the Behavior Change Consortium of the National Institutes of Health, which included: falls, cardiovascular-related episodes, musculoskeletal-related events and health care use. The study was approved by the Institutional Review Board of the institution and was conducted in accordance with a clinical trial protocol registered at ClinicalTrials.gov.

### Interventions and Comparators or Controls

The two study arms received the same CAM intervention, and the comparison was between the on-site delivery (DirectCAM) versus the asynchronous delivery (TeleCAM). The CAM intervention is a 12 week intervention (3 month) composed of 20 sessions that were structured into two segments: the first 8 weeks consisted of two 1-hour sessions per week that included 3 components: 20-minute yoga exercise routine; 20-minute Pilates exercise routine; and a 20-minute routine of dual tasking and functional exercises that involved multifaceted training such as multidirectional upper extremity reaching while carrying on a conversation, and ball bouncing while tracking the ball with head and eye movements. From weeks 9 to 12, the intervention transitioned to one session per week that focused on yoga and Pilates. The intervention was adapted and tailored toward the functional level of each participant, determined by the time it took for participants to complete the Timed 25-Foot Walk (T25FW) test. There were 4 functional levels provided. A participant who had a T25FW score of less than 6 seconds was assigned to TEAMS 1, a T25FW score of 6 to 7.99 seconds was

TEAMS 2, a T25FW score of more than 8 seconds was TEAMS 3, and if unable to complete the T25FW, TEAMS 4 was assigned. If the participant self-reported a diagnosis of osteoporosis and was able to complete the T25FW, they were assigned to TEAMS 3-OP. Those with a diagnosis of osteoporosis that were unable to complete the T25FW were assigned to TEAMS 4-OP. TEAMS 1 and TEAMS 2 completed the intervention exercises in prone, supine, long sitting, standing, and quadriped. TEAMS 3 and TEAMS 3-OP completed the exercises in a chair and with an assistive device for support in standing. TEAMS 4 and TEAMS 4-OP completed all the exercises in a chair. All TEAMS levels included ways to tailor the exercises to better align each participant's functional level. **Figure 2** demonstrates examples of the exercises and adaptation of the CAM intervention.

**Figure 2. Examples of the CAM Intervention Exercise and Adaptation**

Program Component	Sample Content	Modification Examples
Yoga Exercise (20 minutes)	
Tree Pose Standing: 1) Begin in standing. Bring shift your weight to your left side and bend your right knee sliding your foot against your inner thigh to your farthest range 2) Bring your hands into prayer position with your thumbs resting on your chest. 3) Hold this pose for four breaths.
 
Chair: 1) Begin sitting in a chair. Extend your left leg out straight and shift your weight to your left side. 2) Bend your right knee and slide your foot against your inner thigh to your farthest range. 3) Bring your hands into prayer position with your thumbs resting on your chest. 4) Hold this pose for 2 breaths
	
Lower difficulty: Bring the right foot to the left ankle to rest on the toes without sliding up.
 
Higher difficulty: Extend arms out above instead of in prayer position.

Pilates Exercise (20 minutes)	
Spine Twist Long sitting: 1) Start with sitting on the floor with legs extended in front of you and arms open to your sides at shoulder height. 2) Exhale and rotate your torso to the right side (twist); make sure your head and arms follow 3) Inhale and return to starting position. 3) Exhale and rotate your torso to the left side (twist); make sure your head and arms follow
 
Chair: 1) Sitting in a chair with both feet on the floor and arms open at your sides at shoulder height. 2) Exhale and rotate your torso to the right side (twist); make sure your head and eyes follow as well. 3) Inhale and return to starting position. 4) Exhale and rotate your torso to the left side (twist); make sure your head and eyes follow as well.
	
Lower difficulty: Cross arms across chest instead of extended at sides.
 
Higher difficulty: 1) Utilize a TheraBand with arms extended for long sitting exercise challenge 2) Sit on the Pilates disc for chair exercise challenge.
  
Dual Tasking Exercise (20 minutes)	
Dual Tasking: Vision: Smooth pursuits and Vestibular Ocular Reflex exercises; Cognition: Process Speed exercises through alphabet object naming and simple mathematic tasks; Gross and fine motor coordination: Dysdiadochokinesia exercises
 	
Lower Difficulty: 1) Perform same tasks while sitting supported in chair.
 
Higher difficulty: 1) Perform same tasks while sitting on physioball or Pilates Disc; 2) Perform same tasks while standing in partial tandem, tandem or on a Pilates Disc.

Participants were given exercise equipment after baseline testing for the Main Study. Both arms received the same equipment based on their TEAMS level. The TeleCAM arm received a tablet and tablet stand in addition to the exercise equipment. The DirectCAM received the exercise equipment to use at home, and the clinic kept a set of equipment for use at onsite visits. **Table 2** provides an overview of the CAM intervention for the Main study.

**Table 2. Exercise Equipment by TEAMS Level**

Equipment	TEAMS Level 1	TEAMS Level 2	TEAMS Level 3	TEAMS Level 4
Racquet Ball	✓	✓	✓	✓
Yoga Strap	✓	✓	✓	✓
Theraband	✓	✓	✓	✓
Pilates Disc	✓	✓	✓	✓
Sliders	✓	✓	✓	✓
Yoga Mat	✓	✓	✓	✓
Yoga Block	✓	✓	✓	
Physioball	✓	✓	✓	
Half Roll	✓	✓		
Tablet (TeleCAM)	✓	✓	✓	✓
Tablet Case (TeleCAM)	✓	✓	✓	✓
Tablet Stand (TeleCAM)	✓	✓	✓	✓

TEAMS: Tele-Exercise and Multiple Sclerosis, CAM: Complementary and Alternative Medicine, T25FW: Time 25 Foot Walk score. TEAMS level 1: T25FW <6 seconds, TEAMS level 2: T25FW 6-7.99 seconds, TEAMS level 3: T25FW >8 seconds, TEAMS level 4: unable to complete T25FW.

For the Enhancement study, participants received an additional set of equipment (in addition to the exercise equipment) that was shipped to their home for completing the teleassessment protocol. The teleassessment equipment provided to participants in the Enhancement study is outlined in Table 3. For safety considerations, rDirectCAM participants who had a PDDS score of 5, 6, and 7 were not given any tests related to ambulation. Hence, two different sets of equipment were provided: one for participants with a PDDS score of 0-4 and another for participants with a PDDS score of 5-7.

**DirectCAM.** DirectCAM participants were asked to work with a therapist at the assigned clinic to complete the 20 one-hour training sessions as described in **Figure 2**. A therapists training manual and a DirectCAM session checklist were used to ensure intervention fidelity across therapists (see Appendices A and B). At the end of the 12-

week intervention, the DirectCAM participants received a set of instructions and handouts (see Appendix C) with photos demonstrating the exercises and were asked to continue the program in their home for up to one-year post-intervention initiation (i.e., 9 months after the completion of the intervention delivered at the clinic).

**TeleCAM.** The TeleCAM participants received the same intervention content as DirectCAM. The only difference was that the TeleCAM participants received the intervention via exercise videos preloaded to a tablet that was given to them upon enrolling in the study. The exercise videos were filmed with a person with MS instructing and demonstrating the CAM program. Each TeleCAM participant began with one onsite training session with a study therapist. In the training session, participants were shown how to turn the tablet on and off to watch the videos, perform the basic exercises correctly, and use the yoga and Pilates equipment. Participants were asked to bring a family member or friend with them in case they needed assistance using the tablet. The TeleCAM participants were contacted by an Interactive Voice Response (IVR) system-initiated call at their preferred dates and times (aligned with the general intervention timeline) to promote adherence to the yoga/Pilates exercise and neurorehabilitation practice. The IVR system is an automated communication system that includes computers, specialized phone hardware, and operating software to allow immediate computer-assisted interaction with participants by telephone. It was developed during our research team's past physical activity research and in the current study was adapted to address the specific concerns of individuals with MS (physical activity progress, pain, fatigue, and key motivational variables from the SCT). The IVR calls were sent to only

TeleCAM participants weekly for the first six months, and then biweekly for months 6-12 to monitor physical activity, pain, fatigue, and quality of life for SCT variables.

**rDirectCAM.** The rDirectCAM was developed in response to the Covid-19 pandemic and was the Enhancement study intervention. Participants enrolled in rDirectCAM received the same intervention as DirectCAM. The only difference was that the rDirectCAM participants utilized a remote platform at home to work synchronously with a therapist.

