## Analytical and Statistical Approaches

### **Main Study**

Our analysis was following ITT protocol as all participants assigned to the randomized clinics and completed baseline assessment were included in the analysis.

Our primary hypotheses were about comparing the change in the 11 outcomes (listed in **Table 4**) between baseline and 12th month follow-up across the two arms. We considered these 11 hypothesis tests for the 11 outcome variables as part of a single family of hypotheses. We employed the Holm-Bonferroni method for controlling the overall family wise error rate and computed adjusted *p*-values. For each outcome we used a linear mixed effects model, with TeleCAM arm as the reference category, and accounting for the correlated nature of the data due to the nesting of participants within a clinic as random effects. Crude models included fixed effects included both Arms (TeleCAM, DirectCAM), Time (baseline [reference], 3 month, 6 month, 12 month), an Arms X Time interaction, and accounted for randomization strata (clinic location being urban vs. non-urban). The interaction of Arms and Time variables was the primary effect of interest since it quantified the differences within Arm change in the outcome from baseline over time of the two Arms. For example, based on the fitted model that included the interaction between Arm and Time, the difference in change over time from baseline to 12 months between DirectCAM and TeleCAM were estimated. Contrast statements were used to test the null hypotheses in conjunction with the fitted model coefficients and standardized differences in the average treatment effect reported. The estimates of the change in health and function outcomes for each arm and their 95% confidence interval were also reported. As a sensitivity analysis, similar models additionally adjusted for sex, race, and post-COVID data collection measure indicated were also ran. Note that, since post-COVID, data collection for patient reported outcomes was conducted remotely for remaining participants, the former was also included as a covariate in the adjusted model. Next, missingness in primary and secondary outcomes were addressed using multiple imputation technique (MCMC) via PROC MI in SAS,

assuming missing at random. Additional sensitivity analyses were conducted using wild bootstrap to assess the robustness to model assumptions.

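### The plan says the arms differ only in delivery medium, but TeleCAM alone has automated calls scheduled to month 12, so the primary contrast compares packages and does not isolate delivery mode

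*Combined protocol and SAP*

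**What the plan says.** All references are to the Combined protocol and SAP.

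- **Comparison.** The section on interventions and comparators states: "The two study arms received the same CAM intervention, and the comparison was between the on-site delivery (DirectCAM) versus the asynchronous delivery (TeleCAM". Study Overview describes the trial more broadly, as "comparing the effectiveness of TeleCAM and DirectCAM delivered at 43 clinics".
- **TeleCAM paragraph, medium.** "The only difference was that the TeleCAM participants received the intervention via exercise videos preloaded to a tablet".
- **TeleCAM paragraph, calls.** The same paragraph describes Interactive Voice Response (IVR) calls whose stated purpose is to support adherence, with content adapted to activity progress, pain, fatigue and motivational variables from Social Cognitive Theory (SCT). It restricts these calls to one arm and gives their recipients, timing and use as "TeleCAM participants weekly for the first six months, and then biweekly for months 6-12 to monitor physical activity, pain, fatigue, and quality of life". Table 5 lists calls in the TeleCAM column only, up to month 12.
- **DirectCAM paragraph.** Twenty one-hour therapist sessions, then written instructions and photo handouts for exercising at home up to one year from the start. The text before Table 2 adds that DirectCAM participants also had exercise equipment for home use.
- **Primary analysis (Analytical and Statistical Approaches, Main Study).** The primary hypotheses concern change from baseline to month 12, so that "the difference in change over time from baseline to 12 months between DirectCAM and TeleCAM were estimated". The model has arm, time, arm by time, the randomisation stratum and clinic.
- **Mediation (same section).** Social support, outcome expectancies, self-efficacy and self-regulation are tested as mediators between the intervention and the primary outcomes.

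**The concern.** The statement of the comparison and the description of the arms disagree. One says that content is common and only the medium changes. The other gives one arm a year of automated contact that the other arm does not have.

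The disagreement reaches the primary result because the programme ends at week 12 and the primary time point is month 12. For the intervening nine months the arms have different maintenance support. Suppose clinic sessions did better at month 3 and TeleCAM caught up by month 12 with the help of the calls. The 12-month contrast would then be near zero, and a reader relying on the sole-difference sentence would conclude that therapist and video delivery are equivalent. The opposite pattern could be misread in the same way.

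The mediation aim is exposed too. The calls address SCT motivational variables, and the mediators are SCT constructs. An indirect effect through self-efficacy or self-regulation could reflect the calls, the medium or both.

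**Working it through.** **1. The plan's own contact count.** The Interventions section gives two sessions a week for 8 weeks, then one a week for 4 weeks: 8 × 2 + 4 × 1 = 20. This matches the stated 20 sessions. Table 5 labels the two-a-week phase *biweekly*, so in that row the word means twice a week.

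**2. Scheduled IVR calls.** The documents state no total. Use 52/12 = 4.333 weeks per month and read *biweekly* for calls as every two weeks.

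| Source | Weekly phase | Biweekly phase | Total | After month 3 |
|---|---|---|---|---|
| TeleCAM paragraph | 6 × 4.333 = 26 | 6 × 4.333 / 2 = 13 | 39 | 39 − 13 = 26 |
| Table 5 | 5 × 4.333 = 21.7 | 7 × 4.333 / 2 = 15.2 | 36.8, about 37 | 36.8 − 13 = 23.8, about 24 |
| DirectCAM | none described | none described | 0 | 0 |

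Calls in months 1 to 3 under either schedule: 3 × 4.333 = 13. The two totals differ because the paragraph runs weekly calls for six months, whereas Table 5 stops them after month 5.

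**3. Sensitivity to the word biweekly.** Read as twice a week, as Table 5 uses it for sessions, the paragraph gives 26 + 6 × 4.333 × 2 = 26 + 52 = 78. Table 5 gives 21.7 + 7 × 4.333 × 2 = 21.7 + 60.7 = 82.3, about 82. Every reading leaves DirectCAM at none described.

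**4. Share of the primary interval.** The programme takes 3 of the 12 months, so 9/12 = 75% of the interval is maintenance with unequal support.

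**5. What the model can separate.** Let δ3 and δ12 be the arm differences in change from baseline at months 3 and 12. Both come from the arm-by-time terms. Then

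δ12 = δ3 + (δ12 − δ3).

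The first part arises during the programme and the second during maintenance. The primary test uses only the sum, so opposite signs in the two parts can cancel. No term in the model can separate the calls from the medium, because calls are scheduled for TeleCAM and not for DirectCAM.

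**6. Mediation.** In the product-of-coefficients method, path *a* is the effect of arm on the mediator (Figure 3 legend). With arm as the exposure, *a* includes whatever the calls do to the mediator, so *a × b* is an indirect effect of the package.

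**The case against.** The best defence is that the calls belong to TeleCAM. They are disclosed under the TeleCAM heading, Study Overview sets out to compare two named programmes, and automated prompting is a natural part of unsupervised delivery. Randomised clinics then support a valid contrast of the two programmes at month 12. The mediation aim likewise speaks of the intervention, not of delivery mode. This stands. A reader might infer that the primary contrast cannot answer the trial's question, and the documents do not support that. What the defence does not rescue is the sentence declaring a sole difference, or any conclusion drawn from it about medium alone.

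That sentence follows one about common content, so it could be taken to concern exercise content only. Even so, nothing in the comparison statement tells the reader that support also differs.

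Other tempting readings also go too far:

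- **TeleCAM alone kept the videos.** The tablet was given to participants, but neither its return nor video access after month 3 is stated. The point rests on the calls and does not need this.
- **Every call was motivational.** The TeleCAM paragraph also gives monitoring as a purpose, and Data Collection and Sources refers to weekly feedback but monthly motivational data.
- **All extra support went to TeleCAM.** During the programme, therapist contact runs the other way: 20 sessions in DirectCAM against one onsite training session in TeleCAM. DirectCAM also had home equipment.
- **Month 3 gives the clean delivery effect.** It does not, because about 13 TeleCAM-only calls fall before it.

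**Conclusion.** The concern holds as a matter of what may be concluded. The sole-difference statement is contradicted within its own paragraph and by Table 5. The 12-month contrast and the SCT mediation results validly compare packages, and neither isolates delivery mode.

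The size is an imbalance in scheduled calls of about 37 to 39 against none described, with about 24 to 26 after month 3. It assumes that biweekly means every two weeks, and it counts scheduled calls, not answered ones. The documents give no effect size for the calls, so they show neither that a 12-month difference, or its absence, was produced by the calls nor how far a delivery-mode reading would be wrong.

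**What to change.** 1. **Correct the comparison.** Replace the sole-difference sentence with the full components of each arm: for TeleCAM, the tablet videos, the onsite training session, the home equipment and the IVR calls; for DirectCAM, the therapist sessions, then the instructions, photo handouts and home equipment. Define the 12-month estimand as a comparison of these packages. State that neither the primary nor the mediation results may be attributed to delivery mode alone.
2. **Show when a difference arose.** Report the baseline-to-3-month and month-3-to-12 arm contrasts from the fitted model as supporting results outside the Holm family, labelled post hoc if added after the data were seen. State that the first includes about 13 TeleCAM-only calls. State that the second locates a difference in time and does not measure the effect of the calls, since carry-over from the programme also enters it.
3. **Reconcile the descriptions.** Bring the TeleCAM paragraph and Table 5 into agreement on when weekly calls end, define *biweekly* for calls and sessions, and say whether TeleCAM participants had video access after month 3.

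The cost is wording and two contrasts from a model already fitted, with no new data and no charge to the family-wise error rate. The downside is a narrower headline claim.
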